#### 9. Amendments to the CIP

Amendments to the CIP will be agreed upon between the coordinating investigator and the sponsor. Substantial modifications must be approved by the Swedish Ethical Review Authority and/or the Swedish Medical Products Agency before implementation.

### 10. Deviations from the CIP

Investigator(s) are not allowed to deviate from the CIP except if it is for the protection of the subject's rights, safety, or well-being under emergency circumstances. All such emergency deviations shall be documented and reported to the sponsor, the Swedish Medical Products Agency and/or the Swedish Ethical Review Authority (as applicable) as soon as possible.

Any other deviations or waivers from the CIP are not permitted.

All deviations shall be documented with an explanation and reported to the sponsor. Deviations will be reviewed by the sponsor and reported to the appropriate regulatory bodies as required.

# 11. Device traceability and accountability

The investigational device(s) will only be used in the clinical investigation according to the clinical investigation plan. The sponsor provides the site with written instructions and training of DSD.

# 12. Statements of compliance

# 12.1. Compliance to the investigational plan, good clinical practice, and regulations

Version No: 1.1

Date: 2024-10-27 37 (48)

The clinical investigation will be conducted in accordance with the clinical investigation plan, the ethical principles of the Declaration of Helsinki, the principles of SS-EN ISO 14155:2020 and current national and international regulations governing this clinical investigation. This is to ensure the safety and integrity of the subjects as well as the quality of the data collected.

## 12.2. Ethical review of the clinical investigation

The clinical investigation will commence when written approval/favorable opinion from the Swedish Ethical Review Authority has been received and confirmation of validity has been received from the Swedish Medical Products Agency.

The final version of the informed consent form and other information provided to subjects, must be approved or given a written positive opinion by the Swedish Ethical Review Authority or the Swedish Medical Products Agency. The Swedish Ethical Review Authority and the Swedish Medical Products Agency must be informed of any changes in the CIP in accordance with the current requirements.

#### 12.3. Insurance

Swedish Patient Insurance (Patientskadeförsäkring): The Swedish healthcare regions have signed a patient insurance with Landstingens Ömsesidiga Försäkringsbolag, LÖF.

## 13. Informed consent process

## 13.1. General process for informed consent

Informed consent for participating in the study cannot be obtained from the subject at the scene since the victim is unconscious. The cardiac arrest may be witnessed by family members, but to ask for consent form a relative or a legally representative in this scenario is not possible for both practical and ethical reasons. The time window to include and perform the intervention is within minutes. Therefore, informed consent cannot be obtained before the trial intervention.

According to the Helsinki Declaration paragraph 30;

"Research involving subjects who are physically or mentally incapable of giving consent, for example, unconscious patients, may be done only if the physical or mental condition that prevents giving informed consent is a necessary characteristic of the research group. In such circumstances the physician must seek informed consent from the legally authorized representative. If no such representative is available and if the research cannot be delayed, the study may proceed without informed consent provided that the specific reasons for involving subjects with a condition that renders them unable to give informed consent have been stated in the research protocol and the study has been approved by a research ethics committee."

Version No: 1.1

Date: 2024-10-27 38 (48)

According to MDR 2017/745 article 68, it possible to obtain informed consent to participate in a trial after the decision to include the patient if all other circumstances outlined in article 68 are fulfilled:

- The decision to include the patients is done in conjunction with the interventional treatment. The treatment in this trial must be provided during cardiopulmonary resuscitation, within minutes from the cardiac arrest.
- It's not possible to obtain consent prior to inclusion since cardiac arrest is a sudden and unexpected life-threatening emergency event.
- There are scientific reasons to believe that participation in the trial can have direct clinical benefits for the participating patient / study subject.
- There is no possibility to inform or obtain consent from a legally representative since the interventional treatment must be provided within minutes from EMS arrival and during ongoing CPR.
- There is no way for the principal investigator to obtain information that the study subject has expressed an opposing view to participate in the trial beforehand, since cardiac arrest is a sudden, unexpected life-threatening emergency.
- The trial intervention has a direct connection to the medical condition (cardiac arrest) that renders the patient/study subject unable to give informed consent.

## 13.2 Consent process

The chance of surviving cardiac arrest is very low, overall 90% of the patients die. In the OHCA sub-set of patients with VT/VF survival at 30 days is about 30%. In a cardiac arrest scenario treatment of CPR and defibrillation must be started immediately in order to increase the chance of survival.

Due to the nature of the condition of sudden cardiac arrest, informed consent for participating in the study cannot be obtained from the subject at the scene since the victim is unconscious at the time for study inclusion and the EMS personnel or the sponsor has no previous information about the patients willing to participate in the study or not. According to the EU:s Clinical Trials Regulation clinical course in patients that regains circulation after a in hospital cardiac arrest shows a wide variety, from irreversible to reversible circulatory shock, irreversible brain damage and death to neurological intact survival and fast recovery in cognitive functions. Therefore, the strategy for obtaining informed consent varies dependent on patient outcome.

The strategy for obtaining informed consent is as follows according to the patient's status

- 1. The patient who is not regaining circulation and is declared dead at the scene of the arrest. No consent will be obtained
- 2. The patient who survives the initial resuscitation phase, is transferred to hospital and is conscious. Information about the study (both oral and written) will be given during hospital stay. The information includes the purpose of the study, the study intervention, possible risks and benefits from participating in the study and who is legal responsible for the study. In the information it is also clarified that all

Version No: 1.1

Date: 2024-10-27 39 (48)

- participation is voluntary, the right to not participate in the study and the right to withdraw participation. The informed consent is obtained.
- 3. The patient who survives but is not enough conscious, GCS <14, have severe dementia, suffer from expressive and/or impressive aphasia or are unable to write his or her signature. In this case, when the patient is not able to give an informed consent by his or her own, the consent shall as soon as possible be sought after the emergency situation, circulatory shock, (defined as no need for inotropics) is resolved. This informed consent will be sought by the investigator from the patients legally designated representative without undue delay, normally during or after the ICU period. If the patient still is unable to provide informed consent due to cognitive impairment after the ICU period, renewed contact to inform the patient and obtain informed consent as soon as the patient can give informed consent.

If informed consent has been obtained from the legally designated representative, informed consent to continue the participation in the clinical trial shall be obtained from the patient as soon as he or she can give informed consent.

If the incapacitated patient does not have a legally designated representative the investigator has to approach the lawcourt for this purpose.

The informed consent process is performed by local staff at each referring hospital.

The principal investigator shall ensure that the subject is given full and adequate oral and written information about the clinical investigation, its purpose, any risks and benefits as well as inclusion and exclusion criteria.

Subjects must also be informed that they are free to discontinue their participation in the clinical investigation at any time without having to provide a reason. Subjects shall be given the opportunity to ask questions and be allowed time to consider the provided information and participation in the clinical investigation. If the person chooses to participate, both the subject and the investigator shall sign the informed consent form. A copy of the subject information as well as a copy of the informed consent form shall be provided to the subject. The process shall be documented in the subject's source documents and the signed informed consents shall be maintained with the essential documents. If new information becomes available that can significantly affect a subject's future health and medical care, that information shall be provided to the affected subject(s) in written form. If new information is added to the clinical investigation, the subject has the right to reconsider whether he/she will continue their participation.

# 14. Adverse events, adverse device effects and device deficiencies

#### 14.1. Definitions

Version No: 1.1

Date: 2024-10-27 40 (48)

#### 14.1.1. Adverse Event

An Adverse Event (AE) is untoward medical occurrence, unintended disease or injury or any untoward clinical signs, including an abnormal laboratory finding, in subjects, users or other persons, in the context of a clinical investigation, whether or not related to the investigational device.

This definition includes events that are anticipated as well as unanticipated events. This definition includes events occurring in the context of a clinical investigation related to the investigational device, the comparator or the procedures involved.

#### 14.1.2. Adverse Device Effect

An Adverse Device Effect (ADE) is any AE related to the use of an investigational medical device.

This definition includes adverse events resulting from insufficient or inadequate instructions for use, deployment, implantation, installation, or operation, or any malfunction of the investigational medical device.

This definition includes any event resulting from use error or from intentional misuse of the investigational medical device. This includes both the interventional and comparator.

#### 14.1.3. Serious Adverse Event

A Serious Adverse Event (SAE) is any AE that led to any of the following:

- a) death,
- b) serious deterioration in the health of the subject, that resulted in any of the following:
  - i. life-threatening illness or injury,
  - ii. permanent impairment of a body structure or a body function,
  - iii. hospitalization or prolongation of patient hospitalization,
  - iv.medical or surgical intervention to prevent life-threatening illness or injury or permanent impairment to a body structure or a body function,
  - v. chronic disease,
- c) fetal distress, fetal death or a congenital physical or mental impairment or birth defect

#### 14.1.4. Serious Adverse Device Effect

A Serious Adverse Device Effect (SADE) is an ADE that has resulted in any of the consequences characteristic of a serious adverse event.

SAEs related to procedures imposed by the clinical investigation plan but not with the use of the device shall not be considered Serious Adverse Device Effects.

## 14.1.5. Unanticipated Serious Adverse Device Effect

An Unanticipated SADE is an effect which by its nature, incidence, severity or outcome has not been identified in the current risk assessment. Procedures associated with the use of a device shall be addressed in the risk assessment, which makes it possible to determine whether the procedure related SAEs are Unanticipated Serious Adverse Device Effect or not. SAEs related to procedures imposed by the clinical investigation plan but not with the use of the device shall not be considered Serious Adverse Device Effects.

For the anticipated adverse device effects, se section 4.2 above.

Version No: 1.1

Date: 2024-10-27 41 (48)

## 14.1.6. **Device Deficiency**

A Device Deficiency (DD) is any inadequacy in the identity, quality, durability, reliability, safety or performance of an investigational device, including malfunction, use errors or inadequacy in information supplied by the manufacturer.

This includes detected errors at defibrillator self-test after each use.

## 14.2. Recording and Reporting

#### 14.2.1. Recording

The principal investigator or an authorized designee will record:

- all AEs except the events specified not to be recorded
- all SAEs;
- all DDs;
- - any new finding in relation to any of the above-mentioned events.

Events that are related to cardiac arrest and would be expected in patients undergoing attempted resuscitation should NOT be reported. These include:

- Death
- Hospitalization
- Persistent or significant disability or incapacity
- Organ failure

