### 14.2.2. Reporting

The investigators will report all SAEs and DDs to the sponsor, immediately but not later than 3 calendar days after investigation site study personnel's awareness of the event. This includes detected errors at defibrillator self-test after each use.

The sponsor will report to the Swedish Medical Products Agency all of the following reportable events:

- any SAE that has a causal relationship with the investigational device, the comparator
  or the investigation procedure, or where such causal relationship is reasonably
  possible;
- any DD that might have led to a SAE if appropriate action had not been taken, intervention had not occurred, or circumstances had been less fortunate; and
- any new findings in relation to any event referred to above.

Reporting by the sponsor will be done by filling out the "Summary Reporting Form" (MDCG 2020-10/2). The form will be filled in/updated for each reportable event or for new findings/updates to already reported events. The form will be transmitted to the Swedish Medical Products Agency. For events that indicate an imminent risk of death, serious injury, or serious illness and that requires prompt remedial action for other patients/subjects, users or other persons or a new finding to it will be reported immediately, but not later than 2 calendar days after awareness by sponsor of a new reportable event or of new information in relation with an already reported event. Any other reportable events or a new finding/update

Version No: 1.1

Date: 2024-10-27 42 (48)

to it will be reported immediately, but not later than 7 calendar days following the date of awareness by the sponsor of the new reportable event or of new information in relation with an already reported event.

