#### 2. Possible

The relationship with the use of the investigational device or comparator, or the relationship with procedures, is weak but cannot be ruled out completely. Alternative causes are also possible (e.g. an underlying or concurrent illness/ clinical condition or/and an effect of another device, drug or treatment). Cases where relatedness cannot be assessed, or no information has been obtained shall also be classified as possible.

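### The exemption of arrest-related death, hospitalisation, disability and organ failure from reporting conflicts with the duty to report and causality-rate every SAE, and lets the site screen relatedness before any report

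*Protocol*

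**What the plan says.** Section 14.2.1 lists what the investigator records. One item is "all AEs except the events specified not to be recorded". The next is all SAEs, with no exception attached, and all device deficiencies (DDs) follow. The section then adds: "Events that are related to cardiac arrest and would be expected in patients undergoing attempted resuscitation should NOT be reported". Its examples are death, hospitalisation, "Persistent or significant disability or incapacity" and organ failure.

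Section 14.1.3 defines seriousness by outcome: "A Serious Adverse Event (SAE) is any AE that led to any of the following". The outcomes include death, life-threatening illness, permanent impairment and hospitalisation.

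Section 14.2.2 states: "The investigators will report all SAEs and DDs to the sponsor, immediately but not later than 3 calendar days" of site awareness. It repeats no exemption. The sponsor must then report to the authority "any SAE that has a causal relationship with the investigational device", and also SAEs linked, or reasonably possibly linked, to the comparator or the investigation procedure.

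Section 14.2.3 has investigator and sponsor assess causality for each adverse event and place each SAE on a four-level scale. Under the level *possible* it says: "Cases where relatedness cannot be assessed, or no information has been obtained shall also be classified as possible".

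**The concern.** The outcomes that most often make an event serious in this trial are the ones listed as not to be reported. One site could follow section 14.2.2 and report every death; another could follow section 14.2.1 and report none. Both would be following the protocol.

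The order of decisions also matters. The causality scale, with its cautious default, works only on events that enter it. If the site first decides that a death was due to the arrest, neither the sponsor's assessment nor the *possible* default is applied to that death as an SAE. Section 2.2 describes this as, to the authors' knowledge, the first clinical trial of an early DSD strategy, so a consistent record of possibly related deaths has value for the main study.

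**Working it through.** The protocol gives no figure to reproduce here. The check sets the rules side by side and then sizes the exempt category.

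**1. Overlap of the two lists.** Death and hospitalisation appear both in section 14.1.3 and in the exempt list. Disability in the exempt list largely matches permanent impairment in section 14.1.3. Organ failure will usually qualify as life-threatening illness. The exempt list is thus mostly a list of SAEs.

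**2. Does the text resolve the overlap?** In section 14.2.1 the exception is attached to the AE line only; the SAE line has none. The exception speaks of events not to be *recorded*, while the list speaks of events not to be *reported*. Section 14.2.2 has no cross-reference to the list. So no order of precedence is stated.

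**3. What the exemption covers.** It has two conditions: the event is related to cardiac arrest, and it is expected during attempted resuscitation. A death plainly caused by the device meets neither. A death that might be due to the procedure is undecided, and no sentence says who decides or what happens when a link is possible.

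**4. Which harms surface by another route?**

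| Event | Other route | Left open |
|---|---|---|
| Defibrillator fails to deliver energy | DD reported within 3 days (14.2.2); treated as SADE (14.3) | No |
| Pause above 60 s, DSD arm | Flagged as AE and notified to monitor and sponsor (14.3) | The pause is flagged; a following death need not be reported as a related SAE |
| Pause of 60 s or less, DSD arm | None specific | Yes |
| Pause in the control arm | None specific | Yes |
| Harm from the shocks without malfunction | Only if the crew perceives it and enters it in CRF1 (14.3) | Partly |

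Section 4.3 names the interruption during posterior electrode placement as the participation risk and expects that step to take no more than 10 to 15 s. Pauses longer than that, up to 60 s, carry no flag. Section 14.1.4 says an SAE caused by a trial procedure but not by device use is not a SADE. A placement-related death would therefore reach the sponsor as an ordinary SAE, the class that section 14.2.1 lets the site screen out, although section 14.2.2 makes procedure-related SAEs reportable to the authority.

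**5. Size of the exempt category.** Inputs: 40 patients, 30 DSD and 10 standard (6.3.3); 30-day survival in VT/VF of about 1/3 (4.6) or about 30% (13.2). Expected deaths by day 30 = N × (1 − survival).

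- Survival 1/3: 40 × 2/3 = 26.7 (DSD 30 × 2/3 = 20; standard 10 × 2/3 = 6.7).
- Survival 30%: 40 × 0.70 = 28 (DSD 30 × 0.70 = 21; standard 10 × 0.70 = 7).

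This assumes that the general VT/VF figures hold for enrolled patients, who have already had at least one shock, and that there is no treatment effect.

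**The case against.** The case for leaving the text alone has real weight. With about two thirds of patients expected to die, some exemption is sensible. Oversight does not depend on SAE forms alone: section 4.5 describes case-by-case review of every included patient, CRF1 records whether the patient survived the event, defibrillator files are analysed for every case, and the sponsor follows up adverse events perceived by crews. A monitoring plan that is not shown may add detail.

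Three stronger readings might be inferred, and the protocol supports none of them.

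- *That the exemption is absolute and would hide a failed second shock.* It is limited to arrest-related, expected events, and a failed shock surfaces as a DD and SADE.
- *That the trial's safety conclusion rests on a depleted SAE list.* The main safety endpoints in section 6.2.1 are chest compression fraction, measured in both groups, and defibrillator malfunction. Neither is exempt. Death and disability are also collected as tertiary endpoints.
- *That some 27 related deaths would be missed.* The figure is expected total mortality and says nothing about relatedness.

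What remains is that none of these routes requires a causality rating for each death. The case review in section 4.5 does not say so, and endpoint collection is blinded to allocation (6.4, 6.5), so it cannot supply one. The conflict between sections 14.2.1 and 14.2.2 is also untouched.

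**Conclusion.** The contradiction is real and should be corrected, but its consequence is limited. Death counts and the main safety endpoints are not affected. What is affected is causality review and reporting of deaths or disability possibly related to device or procedure when no malfunction or flagged pause was detected: for example after a pause of 60 s or less, or a pause in the control arm. For these, the site judges relatedness before any report, whereas section 14.2.3 gives that judgement to investigator and sponsor and sets *possible* as the default.

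The exempt category would hold about 27 to 28 of 40 patients for death alone, under the assumptions stated above. The number of related deaths among them cannot be derived from the protocol. The conclusion rests on the protocol text; the monitoring plan could narrow the gap in practice but would not remove the conflict in the protocol.

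**What to change.** Reconcile section 14.2.1 with sections 14.2.2 and 14.2.3. Keep the exemption, but make it depend on a recorded rating: a listed event is exempt from reporting only if the investigator has rated it *not related* to device, comparator and procedure under section 14.2.3. An event rated *possible* or higher, or accompanied by a DD or a flagged interruption, follows section 14.2.2. State in section 14.2.2 that the exemption applies on these terms, and use *recorded* and *reported* consistently.

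The cost is one relatedness rating per death or other exempt event, plus some additional 3-day SAE reports where *not related* cannot be supported. Because unassessable cases default to *possible*, that number may not be trivial. The criterion in section 14.2.3 that allows attribution to an underlying illness limits it. No new data collection is needed beyond the rating, and no endpoint changes. If the sponsor regards the change as a substantial modification, section 9 requires approval before it takes effect.
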